9.5 Missing Data

- Use last observation carried forward (LOCF) for missing hourly RASS and VAS if < 10% missing.
- Conduct sensitivity analysis excluding patients with > 20% missing data.

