Study Protocol and Statistical Analysis Plan

Isoflurane Sedation Using AnaConDa® Device with Non-Invasive Ventilation for Acute Exacerbation of COPD

**Protocol version 2.0
Dated 04.12.2022**

1. Protocol Synopsis

Title	Isoflurane Sedation Using AnaConDa® Device with Non-Invasive Ventilation for Acute Exacerbation of COPD
Study Design	Prospective, single-arm, interventional pilot study
Study Population	Adult patients (≥ 18 years) with acute exacerbation of COPD requiring NIV
Sample Size	20 patients (interim analysis after 10 enrollees; final analysis planned on 20)
Intervention	Isoflurane sedation via AnaConDa® device during NIV
Primary Objective	Incidence of intervention failure (intubation or excessive sedation)
Secondary Objectives	Safety (vitals, ABG changes), sedation depth (RASS), patient comfort (VAS)
Duration	24 hours of sedation monitoring; follow-up until discharge or intubation
Ethics Approval	BREC 23/121 (20.03.2023), in accordance with ICH-GCP and Declaration of Helsinki

2. Background and Rationale

Acute exacerbations of COPD (AE-COPD) frequently lead to hypercapnic respiratory failure, where non-invasive ventilation (NIV) reduces intubation and mortality risks. However, NIV intolerance due to agitation or dyssynchrony often necessitates invasive ventilation, with attendant complications. Volatile anesthetics like isoflurane, delivered via AnaConDa®, offer rapid, titratable sedation with bronchodilatory effects and minimal accumulation. Preliminary ICU studies suggest improved hemodynamics and faster recovery with inhalational sedation, but data in the NIV setting are lacking. This pilot protocol aims to assess feasibility and safety of isoflurane sedation via AnaConDa® in AE-COPD on NIV.

3. Objectives

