3.1 Primary Objective

- Evaluate the incidence of intervention failure, defined as either requirement for endotracheal intubation or occurrence of excessive sedation (RASS ≤ -3).

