3.2 Secondary Objectives

- Monitor changes in vital signs and arterial blood gas (ABG) parameters at baseline, 2, 6, 12, and 24 hours.

- Assess sedation depth using the Richmond Agitation-Sedation Scale (RASS) at the same time points.
- Measure patient comfort during NIV via Visual Analogue Scale (VAS, 0–10).

4. Study Design

This single-center, prospective interventional pilot study will enroll consecutive AE-COPD patients requiring NIV. After informed consent, eligible patients receive isoflurane sedation via AnaConDa® integrated into a dual-limb NIV circuit. Continuous safety monitoring will guide dose titration. An interim analysis after 10 patients will inform potential early termination for futility or safety concerns.

5. Study Population

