5.2 Exclusion Criteria

- Hypersensitivity to isoflurane or volatile anesthetics
- History of malignant hyperthermia
- Severe hepatic dysfunction
- Contraindications to NIV (e.g., facial trauma, uncontrolled secretions)
- GCS $<$ 12 or inability to protect airway
- Hemodynamic instability unresponsive to fluids
- Pregnancy or recent upper airway surgery/tracheostomy

6. Intervention

Isoflurane infusion will be initiated at 1.5 mL/h via syringe pump (Infusia SP7s®, Fresenius Kabi). The AnaConDa® device is placed between mask and ventilator Y-piece, with scavenging on expiratory limb. Fresh gas flow (FGF) is set at patient minute ventilation plus 0.5 L/min. Target $F_{et}\%$ (end-tidal concentration) is 0.3–0.5 vol% for light sedation. NIV settings:

- Pressure support: 8–20 cm H₂O (titrated to 10 mL/kg IBW)
- PEEP: 4–6 cm H₂O
- RR: 12–16 breaths/min (I:E 1:3–1:4)
- FiO_2 : 30–40% (titrate to SpO_2 88–94%)

Sedation depth will be adjusted based on RASS, targeting -1 to -2 . Excessive sedation ($\text{RASS} \leq -3$) prompts immediate cessation (failure event).

7. Study Assessments

Assessment	Baseline	2 h	6 h	12 h	24 h
Vital signs (HR, BP, RR)	✓	✓	✓	✓	✓
ABG parameters	✓	✓	✓	✓	✓
RASS	✓	✓	✓	✓	✓
VAS comfort score	✓	✓	✓	✓	✓
Intervention failure	—	✓	✓	✓	✓

8. Safety Monitoring

- Continuous pulse oximetry, ECG, non-invasive BP every 15 minutes for first hour, hourly thereafter.
- Monitor for hypotension ($\text{SBP} < 90 \text{ mmHg}$), bradycardia ($\text{HR} < 50 \text{ bpm}$), respiratory depression ($\text{RR} < 10 \text{ breaths/min}$).
- ABG review for hypercapnia or hypoxemia.
- Report serious adverse events (SAEs) within 24 hours to DSMC.

9. Statistical Analysis Plan

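### The LOCF rule in Section 9.5 has no stop at intubation or cessation and no denominator for its 10% limit, and no planned analysis tests what a missing RASS means for the primary outcome

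*Combined protocol and SAP*

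**What the plan says.** **Missing data.** Section 9.5 has two rules. The first is "Use last observation carried forward (LOCF) for missing hourly RASS and VAS if < 10% missing". The second is "Conduct sensitivity analysis excluding patients with > 20% missing data". The first gives no denominator and no rule for 10% or more. The second counts by patient but does not name the analyses it applies to.

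**Schedule.** Section 3.2 plans to "Assess sedation depth using the Richmond Agitation-Sedation Scale (RASS) at the same time points", which are baseline, 2, 6, 12 and 24 h. The Section 7 table puts RASS and VAS at those five times, so neither is scheduled hourly. Section 3.2 defines the VAS as comfort while on NIV. Section 9.4 compares each later time with baseline by a paired test. The Synopsis gives the duration as "24 hours of sedation monitoring; follow-up until discharge or intubation".

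**Primary outcome.** Section 3.1 has failure "defined as either requirement for endotracheal intubation or occurrence of excessive sedation (RASS ≤ -3". Section 6 says that such a RASS "prompts immediate cessation (failure event". Section 7 lists intervention failure in its own row at 2, 6, 12 and 24 h. Section 9.3 takes the proportion of failures in the ITT population with a 95% Wilson interval, and has no rule for a missing failure status.

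**The concern.** Two matters arise from the same rule.

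First, follow-up ends at intubation, so an intubated patient has no later RASS or comfort score. If those visits count as missing and LOCF runs, the last value on NIV is carried to 12 and 24 h. The paired comparisons with baseline would then include a state that no longer exists for the patients who failed. A patient stopped for RASS ≤ -3 would likewise have the over-sedated value carried forward after isoflurane has ended.

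Second, RASS is one half of the primary endpoint. A patient who has not failed has, by definition, a last RASS above -3. A missing reading in that patient can therefore only be read as no event, whether it is filled by LOCF or left blank. If failure status depends on RASS, the error can go only toward fewer failures, and the plan has no analysis in the opposite direction.

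**Working it through.** **Inputs.** N = 20, 50% reference rate, 30-point reduction (Synopsis, Section 9.1). Five scheduled readings per patient, four after baseline (Sections 3.2 and 7). Limits of < 10% and > 20% (Section 9.5). Wilson interval (Section 9.3).

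**The plan's own figure.** One-sample test of 20% against a fixed 50%, two-sided α 0.05, 80% power: n = [(1.96 × √(0.5 × 0.5) + 0.842 × √(0.2 × 0.8)) / 0.30]² = 19.26, rounded up to 20. The sample size reproduces.

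**When LOCF runs, by denominator.**
- Per patient, scheduled visits: one missing value is 1/5 = 20%, or 1/4 = 25% after baseline. The rule never operates.
- Per patient, 24 hourly readings: at most 2 may be missing (2/24 = 8.3%). Values pass intubation only if it occurs in about the last 2 hours.
- Pooled, scheduled visits: up to 9 of 100 may be missing, or 7 of 80 after baseline. Three patients intubated between 6 and 12 h lose the 12-h and 24-h visits: 3 × 2 = 6, which is 6/100 = 6% or 6/80 = 7.5%. LOCF runs on either count.
- Pooled, hourly: up to 47 of 480. The same three patients lose 13 to 18 readings each, 39 to 54 in all (8.1% to 11.3%), so whether LOCF runs depends on when they were intubated.

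In the pooled scheduled-visit case, 3/20 = 15% of the 24-h RASS and VAS values come from patients no longer on NIV.

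**Effect of LOCF on the failure count.** In an unfailed patient LOCF inserts a value above -3, and in a patient already failed the count is settled. The count is therefore the same with LOCF as with no imputation.

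**Effect of missing RASS on the failure count.** Assume a 24-h risk r of RASS ≤ -3, spread evenly, with missingness unrelated to sedation depth and no other record of the event. The risk per interval is 1 − (1 − r)^(1/k), times the largest number missing within the 10% limit.
- r = 20%: 1 − 0.8^(1/4) = 5.4% per visit, × 7 = 0.38 failures; 1 − 0.8^(1/24) = 0.93% per hour, × 47 = 0.43.
- Range for r, same formula: 10% gives 0.18 and 0.21; 30% gives 0.60 and 0.69.

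This cannot be added in full to the 15% example, because both draw on the same limit. With 6 readings already missing after intubation, only 1 more of 80 (or 3 more of 100) may be missing, and the hidden events fall to 0.05 (or 0.16).

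**What the sensitivity analysis does.** A patient intubated between 6 and 12 h lacks 2/5 = 40% of readings if visits after intubation count as missing, and is dropped. Suppose 6/20 fail, three of them intubated in that interval, and the exclusion is applied to the primary outcome:
- all patients: 6/20 = 30%, Wilson 14.5% to 51.9%
- after exclusion: 3/17 = 17.6%, Wilson 6.2% to 41.0%

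**What a worst-case bound would show.** With 4/20 observed (Wilson 8.1% to 41.6%), one non-failure with a missing reading counted as failed gives 5/20 (11.2% to 46.9%). Two give 6/20 (14.5% to 51.9%).

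**The case against.** A reader might infer that LOCF itself lowers the primary failure rate. The documents do not support that. The count is identical without imputation, so deleting LOCF would not move the primary estimate. No section derives failure from LOCF-filled RASS. Failure has its own row in Section 7, and Section 6 makes RASS ≤ -3 a reason to stop at once, so an event may be recorded even when a scheduled RASS is blank. This stands, and it makes 0.4 failures a ceiling under the stated assumptions, not an estimate.

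A reader might also infer that one hidden event decides whether the trial succeeds, because the Wilson upper limit crosses 50% between 5/20 and 6/20. Section 9.3 sets no success threshold; the 50% in Section 9.1 is a sample-size assumption.

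On carry-forward, the second rule in Section 9.5 counts by patient, which favours reading the 10% limit the same way. LOCF then never runs on scheduled visits. Ending follow-up at intubation could also mean that later visits are not missing at all. Both readings are reasonable, but the text settles neither, and the per-patient reading leaves a rule with no effect on the schedule. It is also fair that the > 20% exclusion would show secondary results without the carried values in the example. It does so by dropping patients who failed.

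Finally, summaries of observed values alone would rest increasingly on patients who did well. That is a fair criticism of simply deleting LOCF, and the fix has to answer it.

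**Conclusion.** The point holds mainly for the secondary outcomes. As worded, the LOCF rule either does nothing on the scheduled visits (limit per patient) or allows values from before intubation to stand for later times (limit pooled). In the pooled case, with three intubations between 6 and 12 h and those visits counted as missing, 15% of the 24-h RASS and comfort values are affected.

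For the primary outcome the defect is an omission. The plan does not say how a missing RASS bears on failure status. If status relies on RASS, the bias is zero or downward: at most about 0.4 of 20 patients, or 2 percentage points, within the 10% limit, given a 20% risk and missingness unrelated to sedation depth. It would be larger if readings are lost while patients deteriorate. The one planned sensitivity analysis does not test this, and could remove early-intubated failures if their later visits count as missing.

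This should be fixed before analysis. It does not invalidate the primary analysis, so it is a should-fix point and not a must-fix one.

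**What to change.** In Section 9.5:
- Delete LOCF. Summarise observed RASS and VAS with the number of patients at each time, and state that values are not carried past intubation or cessation of isoflurane.
- For comfort, add a signed-rank sensitivity analysis that gives intubated patients the worst rank, so that later results do not rest only on those who did well. This fits the signed-rank option in Section 9.4.
- For the primary outcome, keep all ITT patients. Report how many non-failures have a missing scheduled RASS or failure assessment, and add a Wilson interval counting them as failures.
- Reconcile *hourly* with the baseline, 2, 6, 12 and 24 h schedule in Sections 3.2 and 7. If any percentage limit on missing data is kept, state its denominator and whether visits after intubation count.

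The cost is SAP wording and one extra table, with no new data. The downside is a less favourable worst-case bound.

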9.6 Interim Analysis

- After 10 patients, DSMC reviews safety: if > 50% failure or SAE rate > 20%, consider early termination.

10. Data Management and Quality Assurance

- Case report forms (CRFs) will capture all assessments.
- Data entry into secure electronic database with audit trail.
- Regular monitoring visits by Clinical Research Associate (CRA).
- Query resolution within 72 hours.

11. Ethics and Informed Consent

- Approval by Institutional Ethics Committee.
- Conducted per ICH-GCP and Declaration of Helsinki.
- Written informed consent obtained prior to any study procedure.
- Confidentiality maintained; data anonymized.

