9.1 Sample Size Justification

Assuming baseline NIV failure/intubation rate of 50%, a 30% absolute reduction requires 20 patients for 80% power at $\alpha=0.05$ (two-sided). Interim analysis after 10 patients will assess safety and futility.

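### Section 9.6 applies its numerical limits only once, after 10 patients: enrolment can continue after a limit is certain to be exceeded, and no limit covers patients 11–20

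*Combined protocol and SAP*

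**What the plan says.** The trial is a "Prospective, single-arm, interventional pilot study" of 20 patients with one interim look. Section 9.6 gives the only numerical limits: "After 10 patients, DSMC reviews safety: if > 50% failure or SAE rate > 20%, consider early termination". Sections 4 and 9.1 also place the interim analysis after 10 patients and mention no other.

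Between looks, section 8 requires: "Report serious adverse events (SAEs) within 24 hours to DSMC". It attaches no count to those reports.

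The primary endpoint in section 3.1 is intervention failure, "defined as either requirement for endotracheal intubation or occurrence of excessive sedation (RASS ≤ -3". Section 9.1 supplies the planning rates: "Assuming baseline NIV failure/intubation rate of 50%, a 30% absolute reduction requires 20 patients", so the hoped-for rate is 50% − 30% = 20%.

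The document does not define an SAE. It does not say whether intubation or RASS ≤ -3 counts as one, or whether the SAE rate is per patient or per event.

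**The concern.** A limit of more than 20% of 10 patients is certain to be exceeded once a third patient has had an SAE, whether that is patient 3 or patient 10. Under section 9.6 the limit takes effect only at patient 10, so further patients can be exposed after the answer is known. After patient 10 no numerical limit remains for the second half of the trial. This matters because section 2 itself says that data on inhaled sedation during NIV are lacking, and with no control group the DSMC has little else to judge by.

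A secondary question is which events the SAE limit counts. If intubations are reported as SAEs, one event contributes to both limits, at thresholds of 3 and 6. The chance of reaching the SAE limit then depends heavily on a definition that the plan does not give.

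**Working it through.** **1. The plan's own sample size.** Inputs from section 9.1: 50% against 20%, two-sided α = 0.05, power 80%. One-sample normal approximation:

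n = [(1.960 × √(0.5 × 0.5) + 0.842 × √(0.2 × 0.8)) / 0.30]² = [(0.980 + 0.337) / 0.30]² = 19.26, rounded up to 20.

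The stated 20 reproduces, which supports reading 20% as the hoped-for failure rate.

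**2. Limits as counts of patients.**
- At 10: more than 20% means 3 or more; more than 50% means 6 or more.
- At 20: more than 20% means 5 or more; more than 50% means 11 or more.

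**3. Patients treated after the SAE limit is certain to be exceeded.** The true SAE rate p is an assumption, since the plan gives none. Patients are taken as independent, with each outcome known before the next patient starts. Patient k+1 is treated after the third SAE patient if at least 3 of the first k had an SAE. The expected number among the first 10 is therefore the sum over k = 3 to 9 of P(Bin(k, p) ≥ 3).

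| p | Terms, k = 3 to 9 | Sum |
|---|---|---|
| 20% | 0.008, 0.027, 0.058, 0.099, 0.148, 0.203, 0.262 | 0.8 |
| 30% | 0.027, 0.084, 0.163, 0.256, 0.353, 0.448, 0.537 | 1.9 |
| 50% | 0.125, 0.313, 0.500, 0.656, 0.773, 0.855, 0.910 | 4.1 |

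The last term in each row is the chance that the third SAE patient has occurred by patient 9, before the planned look: 26%, 54% and 91%.

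For the failure limit, the same sum with 6 in place of 3 (k = 6 to 9) at p = 50% is 0.016 + 0.063 + 0.145 + 0.254 = 0.48. Nearly all the gain from an earlier trigger is therefore on the SAE limit.

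**4. Chance of meeting each limit at 10 patients (exact binomial).**

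| True rate | 3 or more | 6 or more |
|---|---|---|
| 20% | 0.322 | 0.006 |
| 30% | 0.617 | 0.047 |
| 50% | 0.945 | 0.377 |

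**5. Which events count.** Let f be the share of failures classed as SAEs and q an independent rate of other SAEs (both assumed). With 20% failure, the SAE rate per patient is r = 1 − (1 − 0.20f)(1 − q), and the limit is met with probability P(Bin(10, r) ≥ 3).

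| f | q | r | Probability |
|---|---|---|---|
| 25% | 0 | 0.05 | 1% |
| 50% | 0 | 0.10 | 7% |
| 75% | 0 | 0.15 | 18% |
| 100% | 0 | 0.20 | 32% |
| 100% | 5% | 0.24 | 44% |
| 100% | 10% | 0.28 | 56% |

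With f = 100% and q = 0, the SAE limit is met and the failure limit is not (3 to 5 events) with probability 0.322 − 0.006 = 0.316.

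**The case against.** The strongest reply is that the DSMC is not blind between looks. Section 8 sends it each SAE within 24 hours, with no restriction to the first 10 patients, so it would learn of a third SAE promptly. The action in 9.6 is only to consider termination, and this is a 20-patient pilot. That stands in part: the DSMC would have the information. But nothing tells it that three is the number at which to meet, and a failure not classed as an SAE does not reach it by that route.

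Four stronger readings are tempting, and the document does not support them.

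- *The two limits contradict each other.* They are joined by "or" and lead to a non-binding review. Nothing instructs the DSMC to continue when failure is 50% or less. A lower threshold for serious harm than for failure is an ordinary choice.
- *The SAE limit would be met one time in three if isoflurane works as hoped.* That requires every failure to be an SAE and no other SAE to occur. The plan says neither, and step 5 shows the range. The 20% also comes from a planning rate for NIV failure or intubation, while the primary endpoint adds RASS ≤ -3, so the composite rate could be higher.
- *About four patients would be exposed needlessly.* That figure belongs to a 50% SAE rate only. At 20% it is 0.8.
- *Endpoint events should be taken out of the SAE limit.* They would then fall only under the 6-of-10 limit, which is met 5% of the time at a true 30% failure rate. Excessive sedation is a direct drug effect, so this is a real loss of protection.

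**Conclusion.** The point holds as a cheap improvement to monitoring. The limits apply once, no count triggers a review before that look, and none covers patients 11–20. The avoidable exposure among the first 10 averages 0.8, 1.9 or 4.1 patients at assumed SAE rates of 20%, 30% or 50%, with outcomes known in sequence and the rate counted per patient. The corresponding gain on the failure limit is small.

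The secondary point is conditional. Section 9.6 does not say whether endpoint events count as SAEs. At a 20% failure rate, the chance of meeting the SAE limit runs from 1% to 56% over the assumptions shown, against 0.6% for the failure limit. This is an ambiguity to settle, not evidence that the limits conflict.

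**What to change.** Amend section 9.6 as follows, keeping the plan's percentages.

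1. State that both rates count patients, not events.
2. Convene the DSMC as soon as 3 patients with an SAE or 6 failures have occurred among the first 10, as well as at the planned look. Report failures to the DSMC as they occur, so that the count can be kept.
3. For patients 11–20, apply the same percentages to the planned total: convene at 5 patients with an SAE or 11 failures, cumulatively of 20.
4. State whether intubation and RASS ≤ -3 count toward the SAE rate, and show the DSMC the SAE count with and without endpoint events. Do not remove these events from the SAE limit.

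The cost is a few sentences and possible ad hoc meetings. If the true SAE rate were 20%, a meeting before the planned look would occur with probability 26% (step 3). The count of 5 in 20 would be reached with probability 37%, from P(Bin(20, 0.20) ≥ 5) = 0.370. Each meeting is a review, not an automatic stop. No extra patients or assessments are needed.
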